### 1.2 Primary Study Endpoints

Success Rate of IV Insertion within three allowed attempts

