### 1.3 Secondary Study Endpoints

Total number of attempts and time to successful insertion

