## 7.2 Study Procedures

### 7.2.1 Day of Surgery

After obtaining informed consent, the infant will be randomized to the vein visualization or standard group based on a computer generated number.

Standard anesthesia induction procedures will be used. This includes application of standard ASA monitoring at induction and standard inhalation induction with sevoflurane.

Once the subject is deemed ready for intravenous access attempt, a tourniquet will be applied on the corresponding limb where IV access is contemplated.

For those randomized to the control group (standard technique group), the standard technique for establishing IV access will be used. The standard technique involves directly identifying the vein after application of a tourniquet, cleaning with alcohol and then siting the intravenous catheter.

For those randomized to the vein visualization group, the AccuVein device will be used as an aid to identify the vein after application of a tourniquet. The technique of actual insertion of the intravenous catheter will be the same as the standard technique. The device will be used to better visualize and identify the vein.

If, after 3 needle sticks, IV access has not been established using the technique for the group to which the subject was assigned (standard or vein finder), the care provider will use the other technique (standard or vein finder) to attempt to insert the IV line.

In order to avoid operator variation, the intravenous catheter will be inserted by an experienced pediatric anesthesiologist who is a member of the research team. Currently all the pediatric anesthesia faculty members are familiar with, and have used, the vein finder in case of difficult intravenous access. If a complication develops while attempting to start an IV using the vein finder or standard technique, and a rapid IV access is needed, it will be at the attending anesthesiologist's discretion to perform the IV rapidly with either technique, since our faculty anesthesiologists are proficient with both techniques. Multiple anesthesiologists may attempt the IV simultaneously. This is how we would normally manage this situation and is the standard of care. If this happens we will withdraw the child from the study.

Data to be collected:

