The time to successful IV insertion will be from the first time that the canula touches the skin to until successful IV access; up to 3 attempts. After the 3rd attempt, if still unsuccessful, the alternative technique will be used as rescue. Again, time to successful insertion will be noted. Success at IV will be determined by flushability with 5 ml of sterile normal saline. The site(s) of access will also be recorded.

Medical Record Information: This information will include, but is not limited to: Age, gender, physical status, weight, height, skin color, surgical procedure, presenting underlying conditions and co-morbidities.

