## 8.0 Subject Numbers and Statistical Plan

### 8.1 Number of Subjects

A sample size of 160 patients to include a 15% margin above the number indicated by the sample size determination, to allow for subject withdrawal or situations of incomplete subject data.

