### 8.2 Sample size determination

Assuming 90% success rate with the vein visualization device and 95% confidence level, a sample size of 139 patients would be needed to be enrolled in the study.

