### 8.3 Statistical methods

Sigmastat software will be used for statistical analysis. A p-value<0.05 will be considered significant. For statistical analysis, a chi square test will be used for comparing data on attempts and ANOVA for comparing data on times.

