### 12.2 Potential Benefits to Others

This study should provide evidence of whether the AccuVein vein visualization device can decrease the number of attempts or the time to successful IV insertion in the infant population.

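### Section 8.3 does not say how the ordered number of attempts will be tested; a plain Pearson chi-square would be valid but would ignore the order and usually cost power on that secondary endpoint

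*Combined protocol and SAP*

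**What the plan says.** The primary endpoint (section 1.2) is binary: "Success Rate of IV Insertion within three allowed attempts". The secondary endpoints (section 1.3) are "Total number of attempts and time to successful insertion". Section 12.2 puts the question about attempts in one direction: "This study should provide evidence of whether the AccuVein vein visualization device can decrease the number of attempts".

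Section 8.3 covers the analysis of attempts in one clause: "a chi square test will be used for comparing data on attempts". It sets significance at p<0.05. It gives no categories, no code for a child not cannulated in three sticks, and no trend, rank or ordinal method.

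Section 7.2.1 sets the cap and the switch of technique: "If, after 3 needle sticks, IV access has not been established using the technique for the group to which the subject was assigned", the provider turns to the other technique. Under the data to be collected it adds: "After the 3rd attempt, if still unsuccessful, the alternative technique will be used as rescue". Neither section 7.2.1 nor section 1.3 says whether rescue sticks enter the total.

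**The concern.** The number of attempts has a natural order: one stick is better than two, two better than three, and three better than failure. A Pearson chi-square on those four categories treats them as unordered labels and asks only whether the two distributions differ in any way. The question in section 12.2 is whether attempts go down.

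The wording of section 8.3 fits at least three analyses: a Pearson test on four categories, a chi-square for trend, and a 2x2 test of first-stick success. They can fall on different sides of 0.05 in the same data, so the choice should not be left until the data are seen.

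The endpoint itself is also open. Rescue sticks use the other arm's technique, so counting them mixes both techniques within a child, whichever test is used.

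**Working it through.** **Does the sample size depend on this test?** Section 8.2 begins: "Assuming 90% success rate with the vein visualization device and 95% confidence level", and arrives at 139. A one-proportion precision formula reproduces that if the half-width is taken as 5 points (my assumption; none is stated): 1.96² × 0.90 × 0.10 / 0.05² = 138.3, so 139. Adding the 15% of section 8.1 gives 139 × 1.15 = 159.85, so 160. The test for attempts does not enter.

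**Inputs for the power check.** From the documents: "A sample size of 160 patients" (section 8.1), device success 90% (section 8.2) and p<0.05 (section 8.3). Assumed because not given: 1:1 allocation (80 per arm), a two-sided test, control success S of 70, 75, 80 or 85%, and the distribution of attempts.

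**Pattern A, equal success at each stick.** With q = (1 − S)^(1/3) and p = 1 − q, the categories 1, 2, 3 and not successful have probabilities p, pq, pq² and q³. For S = 75% these are 0.370, 0.233, 0.147, 0.250; for S = 90% they are 0.536, 0.249, 0.115, 0.100.

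**Pattern B, proportional odds.** The control arm is as in A. The device arm is shifted by one odds ratio (3.86, 3.00, 2.25, 1.59) so that success reaches 90%.

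Simulated power, 40,000 trials per case:

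| Control success | 70% | 75% | 80% | 85% |
|---|---|---|---|---|
| A: Pearson, 3 df | 87% | 66% | 37% | 13% |
| A: Wilcoxon | 92% | 76% | 48% | 18% |
| A: trend, scores 1–4 | 94% | 80% | 53% | 20% |
| A: first-stick 2x2 | 74% | 55% | 33% | 13% |
| B: Pearson, 3 df | 98% | 88% | 60% | 22% |
| B: Wilcoxon | 99% | 96% | 77% | 34% |

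From unrounded values, Wilcoxon gains 5.5, 10.3, 11.0 and 4.7 points over Pearson in A, and 1.9, 7.5, 17.0 and 11.9 in B. The 1.9 is a ceiling effect. If only the first stick improves (control 85%), power is 44% for Pearson and 57% for Wilcoxon. With no difference between arms, every test rejects in about 5% of trials.

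**Where the sign reverses** (75% to 90%, 80 per arm):
- Failures become third-stick successes only: Pearson 73%, Wilcoxon 10%. For trend, the mean score differs by 0.15 with standard error √((1.44 + 1.05)/80) = 0.176, so z = 0.85 and power is about 14%.
- Former failures spread proportionally over sticks 1 to 3: Pearson 54%, Wilcoxon 41%. For trend, the difference is 0.345 with standard error √((1.44 + 1.02)/80) = 0.175, so z = 1.97 and power is about 50%.
- The primary 2x2 test has about 72% power in both cases.

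**One table, several answers.** Take control 30/19/11/20 and device 43/20/9/8 (illustrative). Expected counts per arm are 36.5, 19.5, 10 and 14.
- Pearson: 2 × (6.5²/36.5 + 0.5²/19.5 + 1²/10 + 6²/14) = 7.68, 3 df, p = 0.053.
- Trend: p = 0.007.
- Wilcoxon: p = 0.009.
- First-stick 2x2 (30 vs 43 of 80): p = 0.039.
- Primary 2x2 (20 vs 8 failures): chi-square 6.23, p = 0.013.

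**Rescue sticks** (pattern A, 75% vs 90%). Mean sticks with the assigned technique are 1 + q + q² = 2.03 vs 1.68, a difference of 0.35. Suppose rescue continues to success at the other arm's per-stick rate (assumed). This adds 0.25/0.536 = 0.47 and 0.10/0.370 = 0.27, giving 2.49 vs 1.95, a difference of 0.54. Some 20 of 80 control children and 8 of 80 device children would have rescue sticks.

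**The case against.** The plan never describes a four-category Pearson table. A chi-square for trend is also a chi-square test, and under pattern A it does at least as well as Wilcoxon. So the documents show a test left unspecified, not a wrong test chosen. This stands, and it is why the point is conditional.

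The power figures rest on assumed distributions, and their sign depends on the pattern. This also stands. In the reverse cases, however, the benefit lies largely or wholly in the failure rate, which the primary endpoint tests directly. The secondary endpoint adds information on the number of sticks, and there the order matters.

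If the clause on attempts was meant only for the primary endpoint, the secondary endpoint has no named test, and the same addition is needed.

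On rescue sticks, the text is not wholly silent. Section 1.2 speaks of three allowed attempts and section 7.2.1 labels the later ones rescue, which favours leaving them out. The word total in section 1.3 still leaves real doubt.

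A reader might infer that the main comparison is compromised, that false positives are inflated, or that Wilcoxon is the one right choice. None of these is supported. The primary endpoint is binary and suits a 2x2 chi-square, the Pearson test holds about 5%, and a trend test serves as well as Wilcoxon.

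**Conclusion.** The point holds as an avoidable gap in the specification of one secondary endpoint. If number of attempts is tested by a Pearson chi-square on four categories, the test is valid but blind to order. Under consistent shifts towards fewer sticks it gives up about 5 to 17 points of power against Wilcoxon, less where power is near 100%. This rests on 80 per arm, device success 90%, control success 70 to 85% and the two assumed patterns; the documents give no control rate or attempt distribution. The loss does not arise if a trend test was intended, and it reverses when only the failure rate changes. The sample size does not depend on it. In the example table the primary test is still significant, so the main conclusion would not be lost. It is worth correcting because it is cheap and removes a choice that could otherwise be made after seeing the data.

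**What to change.** Keep the 2x2 chi-square for the primary endpoint. Add to section 8.3, choosing one test in advance: *Number of attempts with the assigned technique, coded 1, 2, 3 or >3 (not successful in three, counted before any rescue stick), will be compared between arms by the Wilcoxon rank-sum test* (or *by a chi-square test for trend with scores 1 to 4*).

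Amend section 1.3 to say whether rescue sticks count, so that it agrees with section 8.3. The coding above leaves them out because they use the other arm's technique.

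The cost is one sentence in section 8.3 and a few words in section 1.3. It needs no extra children and no data beyond the attempt count that the endpoint already requires. The downside is the lower power shown above when only the failure rate changes, which the primary endpoint covers.

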## 9.0 Confidentiality, Privacy and Data Management

See the Research Data Plan Review Form

## 10.0 Data and Safety Monitoring Plan

## 11.0 Risks

Loss of confidentiality is a potential risk when conducting human subject search.

Increase in the number of IV access attempts and/or time to successful IV placement.

## 12.0 Potential Benefits to Subjects and Others

### 12.1 Potential Benefits to Subjects

If you are assigned to the vein visualization group, it is possible that the insertion of your IV access line may take less time or need fewer needle sticks, but this is not guaranteed.

### 12.2 Potential Benefits to Others

This study should provide evidence of whether the AccuVein vein visualization device can decrease the number of attempts or the time to successful IV insertion in the infant population.

## 13.0 Sharing Results with Subjects

N/A

## 14.0 Subject Stipend (Compensation) and/or Travel Reimbursements

N/A

## 15.0 Economic Burden to Subjects

### 15.1 Costs

N/A

**15.2 Compensation for research-related injury**  
N/A

## **16.0 Resources Available**

**16.1 Facilities and locations**

Penn State Health, Hershey Medical Center and Penn State Children's Hospital

**16.2 Feasibility of recruiting the required number of subjects**

We perform anesthesia on approximately 9000 children a year and, of these, at least 1000 children belong to the infant age group. Of these 10-20% may have preexisting IV so about 600-800 children will fit the criteria for potential inclusion in the study.

**16.3 PI Time devoted to conducting the research**

[name] is assigned to the children's hospital as part of her normal rotation. [name] is a pediatric anesthesiologist. 70% of her practice includes children.

[name], will have four academic days each month.

**16.4 Availability of medical or psychological resources**

N/A

**16.5 Process for informing Study Team**

Meetings will be held periodically as needed to ensure all research team members are informed about the protocol and their duties. Team emails will also be used to keep team members updated.

## **17.0 Other Approvals**

**17.1 Other Approvals from External Entities**

N/A

**17.2 Internal PSU Committee Approvals**

**Check all that apply:**

- Anatomic Pathology – Hershey only – Research involves the collection of tissues or use of pathologic specimens. Upload a copy of HRP-902 - Human Tissue For Research Form on the “Supporting Documents” page in CATS IRB. This form is available in the CATS IRB Library.
- Animal Care and Use – All campuses – Human research involves animals and humans or the use of human tissues in animals
- Biosafety – All campuses – Research involves biohazardous materials (human biological specimens in a PSU research lab, biological toxins, carcinogens, infectious agents, recombinant viruses or DNA or gene therapy).
- Clinical Laboratories – Hershey only – Collection, processing and/or storage of extra tubes of body fluid specimens for research purposes by the Clinical Laboratories; and/or use of body fluids that had been collected for clinical purposes, but are no longer needed for clinical use. Upload a copy of HRP-901 - Human Body Fluids for Research Form on the “Supporting Documents” page in CATS IRB. This form is available in the CATS IRB Library.

- Clinical Research Center (CRC) Advisory Committee – All campuses – Research involves the use of CRC services in any way.
- Conflict of Interest Review – All campuses – Research has one or more of study team members indicated as having a financial interest.
- Radiation Safety – Hershey only – Research involves research-related radiation procedures. All research involving radiation procedures (standard of care and/or research-related) must upload a copy of HRP-903 - Radiation Review Form on the “Supporting Documents” page in CATS IRB. This form is available in the CATS IRB Library.
- IND/IDE Audit – All campuses – Research in which the PSU researcher holds the IND or IDE or intends to hold the IND or IDE.
- Scientific Review – Hershey only – All investigator-written research studies requiring review by the convened IRB must provide documentation of scientific review with the IRB submission. The scientific review requirement may be fulfilled by one of the following: (1) external peer-review process; (2) department/institute scientific review committee; or (3) scientific review by the Clinical Research Center Advisory committee. NOTE: Review by the Penn State Hershey Cancer Institute Scientific Review Committee is required if the study involves cancer prevention studies or cancer patients, records and/or tissues. For more information about this requirement see the IRB website at: <http://www.pennstatehershey.org/web/irb/home/resources/investigator>

## 18.0 Multi-Site Research

### 18.1

N/A

## 19.0 Adverse Event Reporting

### 19.1 Reporting Adverse Reactions and Unanticipated Problems to the Responsible IRB

In accordance with applicable policies of The Pennsylvania State University Institutional Review Board (IRB), the investigator will report, to the IRB, any observed or reported harm (adverse event) experienced by a subject or other individual, which in the opinion of the investigator is determined to be (1) unexpected; and (2) probably related to the research procedures. Harms (adverse events) will be submitted to the IRB in accordance with the IRB policies and procedures.

## 20.0 Study Monitoring, Auditing and Inspecting

### 20.1 Auditing and Inspecting

The investigator will permit study-related monitoring, audits, and inspections by the Penn State quality assurance program office(s), IRB, the sponsor, and government regulatory bodies, of all study related documents (e.g., source documents, regulatory documents, data collection instruments, study data etc.). The investigator will ensure the capability for inspections of applicable study-related facilities (e.g., pharmacy, diagnostic laboratory, etc.).

## 21.0 Future Undetermined Research: Data and Specimen Banking

N/A

